## 5.2 Handling of Study Interventions

Participants will be informed that they could be randomly assigned to 1 of 2 different supportive treatments with a general description of what they will involve (i.e., counseling, gentle movement, writing, and/or relaxation strategies). Information about both arms will be revealed to participants after completion of data collection.

**Measurement of intervention fidelity.** Recommended steps will be taken to ensure treatment fidelity of the videoconference session for both groups to increase reproducibility. The PI and expert yoga therapist ([name]) will train the interventionists to guide participants on the eMMB. The PI and [name] will train the interventionists on the AC. All sessions will be recorded and 20% randomly selected for review by [name] (eMMB) or [name] (AC). Further, the interventionists and [name] or [name] will meet monthly by phone to support them in maintaining familiarity with the protocol.

## 5.3 Concomitant Interventions

### 5.3.1 Allowed Interventions

All participants will continue with routine treatment of medical conditions including medications.

### **5.3.2 Required Interventions**

No additional interventions are required except for those proposed in the protocol.

### **5.3.3 Prohibited Interventions**

There will be no prohibited medications among patients in this study. Prior approval of participation in other behavioral intervention studies is required.

## **5.4 Adherence Assessment**

Adherence will be assessed by: (1) Completion of the videoconference session; (2) any additional contact with the interventionists; (3) use of the self-directed intervention: measured daily for up to one week before and one week after surgery as assessed in another yoga study and self-reported retrospectively (in the past week) at postoperative weeks 2 and 4. Instructors will directly observe and document adherence to the videoconference session. We will consider adequate adherence to protocol if 70% participants complete the planned video conferencing session one day of home practice before and 3 or more days of home practice per week for the two weeks following surgery.

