## 4.3 Study Enrollment Procedures

Individuals scheduled to undergo surgery for suspected gynecologic malignancies (i.e., uterine, ovarian) will be recruited from the Wake Forest Baptist Comprehensive Cancer Center (WFCCC). To identify potential patients, the Project Manager will screen appointment lists and communicate with attending physicians regarding patients' potential eligibility for the trial. Subject recruitment will be documented in a Screening Log including reasons for ineligibility, eligible patients approached, number who declined participation, and number successfully recruited.

If the patient is interested and referred by the physician, the Project Manager will approach or call interested patients prior to surgery to explain the protocol, answer questions, determine eligibility, and discuss informed consent. After making sure the patient clearly understands the study procedures and agrees to follow them, the patient will be asked to sign the informed consent form electronically or in person. If signed electronically, patients will be asked to send the form back to us by a secure means (e.g., REDCap). In the case that the patient is consented electronically, either a hard copy or email attachment of the informed consent document will be provided to the participant. (Appendix A: Informed Consent Document). The original copy will be kept in the participant's file. Each participant will be asked to separately agree to be audio recorded for the study, which will not affect their ability to participate. If they do consent to be videotaped, they are told in the consent form that they can ask not to be included in the filming or withdraw their consent to be videotaped at any time. These videos are focused on the interventionist for the sole purpose of increasing treatment fidelity.

Eligible participants enrolled in the study will be randomized after baseline assessments to the eMMB or AC prior to surgery.

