**Dose and Implementation of eMMB.** A 20-minute eMMB video will be saved as a local file on study tablets and/or will be accessible via the internet (participants will be given the option to receive a link to the study video via email). Participants will also be given a written description of the eMMB practice. Although guidance (i.e., supportive accountability) is important in promoting adherence to eHealth interventions, one study of a stress-management intervention found that adherence-focused guidance (e.g., email reminders, guidance upon request by participants) was as good as more resource intensive content-focused guidance. Thus, in the proposed study, participants will be given the video before surgery and asked to watch it at least once before the procedure. The yoga instructor will call participants before surgery to initiate additional guidance upon request at any time throughout the study and meet with the participant via videoconferencing using Cisco WebEx in the privacy of the hospital room the day following surgery (postoperative day 1 or as soon as feasible). Cisco WebEx supports compliance with the administrative and physical safeguards sections of the final HIPAA Security Rules. The yoga instructors' contact information will be provided with the intervention materials indicating their hours of availability and expected response time. Instructors will attempt to call participants 2 times prior to surgery without leaving a message. Participants will be given an option to communicate with instructors via text messaging from a Medical Center device to increase convenience of scheduling. Meeting live via videoconference will allow yoga instructors to see participants and ensure that they feel comfortable completing the movements postoperatively. The videoconferencing session will be facilitated by the Project Manager and will be audio recorded. If problems transmitting the live intervention occur or it is not possible to complete the intervention in the clinical setting, we will have the interventionist lead the intervention and answer questions by telephone. Participants will be asked to continue to use the video daily for two weeks following surgery and as long as they choose thereafter. The Project Manager will monitor patient-reported self-directed use of the video and call to check in with all participants after the first two days. This dose of content-focused guidance is similar to that found to be effective in other brief or primarily self-directed interventions. For example, hypnosis implemented during one 15-minute pre-operative in-person session, with instructions for how patients could use hypnosis on their own, reduced postoperative pain in women undergoing breast cancer surgery. A self-directed approach may also empower participants to establish self-regulation strategies.

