
**Attention Control (AC).** An AC group focused on providing caring attention will be employed to account for the added time, attention, interaction with an interventionist, and efficacy expectations of the eMMB as recommended for the study of mind-body practices and used in previous studies. In addition, the interventionist will ask patients to write brief diary entries once before surgery and daily for two weeks following surgery. A diary form will be saved as a local file on study tablets via the

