### **Baseline Assessments**

For participants who have successfully been screened for eligibility and are enrolled into the study, baseline assessments will be performed. The baseline assessment may be completed within two weeks prior to surgery.

- *Assessment Completion/Retention.* Percent completion of planned standard and daily assessments.
- *Pain.* The Patient Reported Outcomes Measurement Information System (PROMIS) measure of pain of intensity (i.e., How would you rate your pain on average?), which has been adapted for assessing pain on a numeric rating scale from 0 (no pain) to 10 (worst imaginable pain) “in the last day,” is the proposed primary outcome (at 2 weeks) for the future larger clinical trial that will be informed by the current study. Patient-reported pain is considered the ‘gold standard’ for pain assessment since pain is a subjective experience and PROMIS is supported by the NCCIH and National Cancer Institute. Pain interference, the affective dimension of pain, and analgesic use will be assessed using 9 patient-reported items. *Pain interference* will also be assessed with a PROMIS measure (6-items). The *affective dimension of pain* will be assessed with one item on a scale from 0 (not bad at all) to 10 (the most unpleasant feeling possible for me). *Analgesic use* in the past 24-hours will be tracked daily for one week before and one week post-surgery (postoperative day 1 to 8; day added since participants may report information from the prior day) and converted to a cumulative analgesic consumption score for analysis (2-items). We will also ask participants if they are taking any analgesic medication postoperatively.
- *Sleep Disturbance* will be assessed with a PROMIS Sleep Disturbance short-form (8-items) adapted for daily use.
- *Psychological Distress.* The PROMIS Depression (8-item) & Anxiety (7-item) adapted short-forms will be used to assess psychological distress “in the last day.”

- *Pain Self-Efficacy* will be assessed with the pain management subscale of the Chronic Pain Self-Efficacy Scale, which has been used postoperatively (5-items).

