### Randomization

Randomization will occur the same day that screening is confirmed. Instructions for completing the intervention will begin at the same visit.

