#### 6.2.4 Follow-up Visits

The timing of study assessments is summarized in Table 1. Postoperative day 1 assessments may be completed within 3 days after surgery. The two-week and 4-week assessments can be timed with in-person follow-up visits, which may be

scheduled within a week of the scheduled assessment. Descriptions of additional measures not assessed at baseline include:

- *Adherence.* Completion of the videoconference session
- *Interventionist Communication.* Any additional contact with the interventionists.
- *Intervention Home Practice.* Use of the self-directed intervention (time and duration) will be measured daily for up to one week before and one week after surgery as assessed in another yoga study. Self-reported time of practice will also be assessed retrospectively (in the past week) at postoperative weeks 2 and 4.
- *Acute Adverse Events.* Participants will also be asked to complete two Visual Analogue Scale items assessing pain intensity and psychological distress daily with the instructions to report their experience “right now,” immediately before and after the intervention to detect any acute adverse events.
- *Expected Benefit.* The HEAL Treatment Expectancy measure 6-items) will assess expected benefit of the intervention following the videoconference session.
- *Daily Symptoms* will be assessed for up to one before surgery and week after surgery starting on postoperative day 1 (or as soon as feasible) for 8 days (since participants may report information from the prior day) using 3 items on pain, disturbed sleep, and distress. The same PROMIS pain intensity item will be asked and sleep disturbance and psychological distress items will be used from the MDASI, which asks about each symptom at “its worst” in the past 24 hours from the MDASI designed to be implemented daily and used perioperatively.

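### Pre-surgery home practice is recorded for at most one week, although the materials can be in hand for about two, so early practice that counts towards the Section 5.4 adherence criterion may be missed

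*Combined protocol and SAP*

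**What the plan says.** **What participants are asked to do before surgery.** Section 5.1 says of the eMMB arm that "participants will be given the video before surgery and asked to watch it at least once before the procedure". The attention control (AC) arm is asked to "write brief diary entries once before surgery and daily for two weeks following surgery". Neither request is tied to a particular day before surgery.

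**When they can do it.** Section 6.2.2 (Baseline Assessments) states: "The baseline assessment may be completed within two weeks prior to surgery". Section 4.3 states: "Eligible participants enrolled in the study will be randomized after baseline assessments to the eMMB or AC prior to surgery". Section 6.2.2 (Randomization) adds: "Instructions for completing the intervention will begin at the same visit".

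**What is recorded.** Section 5.4 lists "use of the self-directed intervention: measured daily for up to one week before and one week after surgery", and Section 6.2.4 repeats that use "will be measured daily for up to one week before and one week after surgery as assessed in another yoga study". The only other practice measure is a recall item: "Self-reported time of practice will also be assessed retrospectively (in the past week) at postoperative weeks 2 and 4". The schedule in Section 6.1 has a questionnaire at Day 1 but no home-practice entry there.

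**How it is used.** Section 5.4 calls adherence adequate if 70% of participants complete the video session, one pre-surgery practice day, and at least 3 practice days in each of the two weeks after surgery. Section 9.6 tests an adherence rate against 70%.

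**The concern.** After surgery the two measures join up: the daily survey covers the first week and the Week 2 recall covers the second. Before surgery nothing plays the part of the recall item. Practice on days -14 to -8 satisfies the request in Section 5.1 but falls outside every measure that Section 5.4 names.

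Adherence is one of the primary feasibility outcomes (Section 9.5.1), and Section 9.2 says that a larger study may not be feasible if adherence and retention fall below 70% and recruitment below 50%. Pre-surgery delivery also matters for the choice of format. Section 2.2 reports that five women received the in-person session before surgery, against seven on each postoperative day, and gives the difficulty of consistent pre-surgery delivery as the reason for trying eHealth. If early practice goes unseen, the new format can look less well followed than it was, on the component it was meant to improve.

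**Working it through.** **1. The plan's own figures.** The plan gives no number for this gap. Its precision figures in Section 9.2 (N = 31) do reproduce with the normal approximation, half-width = z × √(p(1−p)/31):
- Two-sided at p = 0.5: 1.96 × √(0.25/31) = 17.6% (plan: 18%).
- One-sided at p = 0.5: 1.645 × √(0.25/31) = 14.8%; at p = 0.9: 1.645 × √(0.09/31) = 8.9% (plan: 9-15%).
- One-sided lower limit at 80%: 0.80 − 1.645 × √(0.16/31) = 68.2% (plan: 68.2%).

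**2. The unrecorded window.** Longest time with materials: about 14 days (Section 6.2.2). Longest recorded period: 7 days (Section 5.4). Difference: 14 − 7 = 7 days, that is days -14 to -8.

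**3. Who can be affected.** Only a woman who (a) was randomized more than 7 days before surgery, (b) practised before surgery only before day -7, and (c) met the other parts of the composite. Anyone randomized within 7 days, or who practised again in the last week, is untouched by the window.

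**4. Effect on the recorded rate.** Let m be the share of truly adherent women who are missed. Then recorded rate = true rate × (1 − m), which can only fall. The rate drops below 70% when m exceeds 1 − 0.70/true rate:
- True 80%: 1 − 0.70/0.80 = 12.5%.
- True 90%: 1 − 0.70/0.90 = 22.2%.

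**5. Chance that the observed rate reaches 70%.** 0.70 × 31 = 21.7, so at least 22 of 31 are needed. This is the benchmark for the point estimate, not the power of the binomial test. Binomial tail P(X ≥ 22), n = 31, with the true rate and m both assumed:

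| m | Recorded rate, true 80% | P(≥22/31) | Recorded rate, true 90% | P(≥22/31) |
|---|---|---|---|---|
| 0% | 80% | 92.5% | 90% | 99.9% |
| 5% | 76% | 81.0% | 85.5% | 99.0% |
| 10% | 72% | 63.8% | 81% | 94.4% |
| 20% | 64% | 27.1% | 72% | 63.8% |
| 30% | 56% | 6.5% | 63% | 23.4% |

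**6. What would produce a given m.** m = e × q, where e is the share randomized more than 7 days ahead and q is the share of those whose only practice came before day -7. Neither is in the documents. At a true 80%:
- e = 25%, q = 25%: m = 6.25%, recorded 75%, P = 77.1%.
- e = 50%, q = 25%: m = 12.5%, recorded 70%, P = 54.2%.
- e = 50%, q = 50%: m = 25%, recorded 60%, P = 14.3%.

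**The case against.** **Scoring is undefined.** A reader might infer that women who practised as asked will be scored non-adherent. The documents do not say so; they leave unrecorded practice without a scoring rule. The supportable statement is that such practice may be missed.

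**More than one use is likely.** The eMMB request is for at least one viewing, not exactly one, and repeat use in the last week removes the problem. This stands and limits m.

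**Other records exist.** An AC diary entry can be held in REDCap with its date (Sections 5.1, 6.2), so the gap is mainly in eMMB, although paper diaries are also allowed. The Project Manager follows reported video use, the instructor telephones before surgery, and Sections 6.2.4 and 7 mention ratings around each practice and home practice logs. Section 5.4 names none of these as the source for the pre-surgery component, and the ratings and logs are described for adverse events.

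**The tested rate may be something else.** Sections 6.1 and 6.2.4 use the term adherence for the video session alone and list home practice separately. If Section 9.6 tests that rate, this gap does not affect the test. Week 2 retention is in any case the stated primary sign of success (Section 1.1). This stands, and is itself something to settle.

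**Large effects are not supported.** A reader might assume lead times spread evenly over 1-14 days and practice only on the day of randomization, giving a miss of 7/14 = 50% and a recorded 80% × 0.5 = 40%. Nothing in the documents supports either assumption; two weeks is a permitted maximum. Nor should the 68% and 86% survey compliance in Section 6.2 be used to add a further loss: both come from earlier studies, and the 68% refers to assessments after surgery.

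**Conclusion.** The mismatch is in the text: up to about 14 days of access, at most 7 days of recording, and no recall item that covers the difference. On the Section 5.4 composite it biases recorded adherence in one direction, downwards, and mainly in eMMB. It could therefore also distort the exploratory comparison of non-adherent participants by intervention group in Section 9.6.

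The size cannot be determined, because the time from randomization to surgery and the timing of practice are not given. The results in the table are conditional on an assumed true adherence and an assumed miss. They show only that a modest miss could matter with 31 participants: at a true 80%, anything above 12.5% is enough to bring the expected rate under the benchmark, while at a true 90% it takes more than 22.2%. The consequence for the formal test depends on which definition of adherence Section 9.6 uses.

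**What to change.** **Measurement.** Record use from the day the materials are given. Alternatively, add one item at the existing Day 1 contact asking on how many days before surgery the participant used her assigned home practice since receiving it. The item should be arm-specific and mention only her own materials, since Sections 5.2 and 6.2.3 withhold the other arm's description until data collection ends. It should be self-completed or asked by the Project Manager, who already knows the assignment, and not by the blinded assessor.

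**Scoring.** Score the pre-surgery component from randomization to surgery. Count it as met if this item or any pre-surgery daily survey shows at least one use. Apply the same rule in both arms; adding dated AC diary entries as a further source would give one arm an extra chance to qualify.

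**Text of Section 5.4.** State that these are the data sources, that a missing daily survey is not by itself a day without practice, and whether the adherence rate tested against 70% is this composite or the video session alone.

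**Cost.** One questionnaire item and a few sentences, with no extra visit. The drawback is a self-report recall of up to two weeks, made shortly after surgery, which is longer than the one-week recall used at Weeks 2 and 4.

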## 6. STUDY PROCEDURES

### 6.1 Schedule of Evaluations

Assessment	Screening : (Day-14 to Day -1)	Baseline, Enrollment, Randomization: (Day 0)	Week 0	AC or eMMB (Day1)	Week1	Week 2	Follow-up (Week 4)
Inclusion/Exclusion Criteria	X						
Communication with Provider	X						
Informed Consent Form		X					
Enrollment/Randomization		X					
Demographics		X					
Clinical Data		X					X
Questionnaire		X		X		X	X
Daily Survey			X		X		
Actigraphy			X		X		
Treatment Fidelity				X			
Intervention Home Practice			X		X	X	X
Adherence				X			
Interventionist Communication			X		X		
Adverse Events				X		X	X
Interview							X

**Note.** AC = Attention Control; eMMB = EMindful Movement and Breathing

## 6.2 Description of Evaluations

To minimize burden, assessments, and interviews will be implemented while patients are at home or already on site for standard care. At the time of enrollment, participants will be provided a tablet computer to borrow for the study (unless they already have a comparable device that they prefer) and receive training on completing questionnaires either online or by telephone, similar to a training successfully implemented in a study of symptom monitoring in this patient population. This prior study suggested that alternate data collection methods such as automated telephone calls may increase adherence to web-based symptom reporting. Patient-reported questionnaires will be conducted at four time points: before surgery (baseline), one day after surgery, two weeks after surgery and 4 weeks after surgery.

We are most interested in assessing and then effectively managing acute within one week following surgery when pain is likely to be highest, and how pain management during this period may ultimately impact longer-term pain. Daily diaries are one method for measuring an experience in a participant's natural setting with low patient burden. Thus, participants will also be asked to complete daily surveys of outcomes and adherence to home practice of the intervention via REDCap and wear a wrist actigraphy device for up to one week before and one week following surgery. REDCap is a flexible electronic data capture system offered by the Wake Forest CTSI that will verify the date and time of assessments implemented via the internet, telephone, or paper. Our team has piloted the use of REDCap for implementing daily assessments during our ongoing study. Women with gynecologic malignancies have demonstrated reasonable compliance (86%) with electronic diary assessment and daily assessments after gynecologic oncology surgery (68% compliance). Participants will be prompted to complete the surveys (3-5 minutes) at approximately 6:00pm each evening and can complete the survey any time before they go to sleep. A paper guide with response options for the questionnaire will be provided to improve comprehension over the telephone. Participants will also be given a wrist actigraphy device and instructions for its use during this same time period.

In addition, demographic data will be patient-reported at baseline, medical records will be reviewed to obtain clinical data, treatment fidelity observed at the videoconference intervention session, and an interview conducted at a follow-up clinic visit or by telephone. Participants will be compensated up to \$100 total for completing study assessments. We will also track recruitment, adherence to the videoconference intervention, any other contact with interventionists, completion of assessments, and any adverse events that may occur. Those who decline participation or drop out of the study will be asked for feedback about their choices.

